7.5.3.3.1 Prohibited Medications

To be eligible for the study, subjects must agree to discontinue use of certain medications for the indicated timeframe prior to enrollment. These medications will remain prohibited throughout the conduct of the study. Any subject who resumes or requires the use of any of these medications during the 144-week treatment period will be discontinued from the study.

- PTH suppressors (e.g., Sensipar®, cinacalcet, calcimimetics) within 2 months before Screening and during the study
- Active pharmacologic vitamin D metabolites or analogs (e.g., calcitriol, doxercalciferol, and paricalcitol), phosphate, or aluminum hydroxide antacids (e.g., Maalox® and Mylanta®) within 21 days before Screening or during the study
- Any mAb therapy (other than study drug)

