9. Have any condition, which in the opinion of the investigator, could present a concern for either subject safety or difficulty with data interpretation, or that places the subject at high risk of poor treatment compliance or of not completing the study.

INVESTIGATIONAL PRODUCT(S), DOSE AND MODE OF ADMINISTRATION:

KRN23 is a sterile, clear, colorless, and preservative-free solution in single-use 5-mL vials containing 1 mL of KRN23 at a concentration of 10 mg/mL or 30 mg/mL. KRN23 will be administered SC without dilution. Subjects will receive study drug via SC injection to the abdomen, upper arms, and thighs; the injection site will be rotated for each visit, with the option to include a different quadrant of the abdomen. No more than 1.5 mL may be administered in a single injection. If a subject needs more than 1.5 mL per administration, multiple injections must be administered. During a visit with multiple injections, the injection site must be different for each administration, but may be in the same general location (eg arm, thigh). After proper training by study personnel in SC injection technique, the subject may self-administer KRN23 or the subject's caregiver may self-administer KRN23 to the subject without supervision of a home health nurse. Starting doses will be individual for each subject, i.e., the

subject's last dose in study KRN23-INT-001 or KRN23-INT-002 (0.3, 0.6, or 1.0 mg/kg). Up to Week 12, individual subjects who have not reached serum phosphorus levels above the LLN (2.5 mg/dL) at the end of the dose interval may have their doses titrated every 4 weeks (i.e., from 0.3 to 0.6 mg/kg or from 0.6 to 1.0 mg/kg) to a maximum dose of 1.0 mg/kg based on fasting trough serum phosphorus levels. Doses may be titrated downward (i.e., from 1.0 to 0.6 mg/kg or from 0.6 to 0.3 mg/kg) if at any point serum phosphorus increases above the ULN (4.5 mg/dL). The investigator will discuss with the medical monitor the need for dose titration.

REFERENCE THERAPY(IES), DOSE AND MODE OF ADMINISTRATION:

The study design is open-label; all subjects will receive investigational product. No placebo or reference therapy will be administered in this study.

DURATION OF TREATMENT:

The treatment duration will be a maximum of 184 weeks (+ 5 days) with a maximum total of 46 doses administered.

CRITERIA FOR EVALUATION:

Safety and Immunogenicity:

Safety assessments will be summarized at Baseline and at each observed time that they are collected.

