7 INVESTIGATIONAL PLAN

7.1 Overall Study Design and Plan

This study is a Phase 2b, open-label, long-term extension study of the completed studies KRN23-INT-001 and KRN23-INT-002 in adult subjects with XLH. The study population will consist of approximately 20 eligible subjects who participated in KHK's study KRN23-INT-001 or study KRN23-INT-002 (received at least 2 doses of KRN23).

Subjects who were discontinued from KRN23-INT-001 or KRN23-INT-002 due to a TEAE classified as possibly or probably related to treatment may be eligible for participation in this study based on the clinical judgment of the investigator with agreement from the sponsor. The study will be conducted over a minimum of 164 weeks and a maximum of 192 weeks, depending on the date of subject entry, to assess the long-term safety, immunogenicity, PD, and clinical efficacy of KRN23.

Subjects will discontinue oral phosphate and active vitamin D metabolite or analog therapy at least 21 days prior to the Screening Visit, will discontinue use of any medication to suppress PTH within 2 months prior to the Screening Visit, and may not resume any of those medications for the duration of the study. Subjects will be brought in for a Screening Visit and asked to provide written informed consent (Section 8.1.3). The Screening Visit will include full medical history and demographic assessments, clinical laboratory testing (blood and urine), a renal ultrasound, and review of all inclusion and exclusion criteria to confirm eligibility.

After eligibility is confirmed, Baseline assessments can occur within 1 day and up to 7 days of the Screening Visit and the tests may be spread out over 2 days. Baseline assessments will include a PHEX mutation analysis for genotype/phenotype correlations, clinical laboratory testing (blood and urine), a physical examination, height and weight, functional and PRO assessments, ECHO and ECG, and Baseline imaging (X-rays). If the Baseline result for PHEX mutation analysis is negative or inconclusive (i.e., No Mutation, Likely Benign, Variant of Uncertain Significance, or Possibly Pathogenic) and the subject provides informed consent, reflexive genetic testing will be performed to assess additional genes associated with phenotypes overlapping with XLH.

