7.3.3 Removal of Subjects from Therapy or Assessment

In accordance with the Declaration of Helsinki, subjects have the right to withdraw from the study at any time for any reason. The investigator may withdraw a subject at any time at their discretion. Ultragenyx must be notified of all subject withdrawals as soon as possible.

Ultragenyx also reserves the right to discontinue the study at any time for either clinical or administrative reasons and to discontinue participation of an individual subject or investigator due to poor enrollment or noncompliance, as applicable.

Subjects may be removed from the study for the following reasons:

- Occurrence of an unacceptable adverse event (AE)
- An illness that, in the judgment of the investigator or Ultragenyx, might place the subject at risk or invalidate the study
- At the request of the subject, investigator, or Ultragenyx, for administrative or other reasons
- Protocol deviation or noncompliance

If the reason for removal of a subject from the study is an AE, the AE and any related test or procedure results will be recorded in the source documents and transcribed onto the electronic Case Report Form (eCRF). AEs should be followed until the abnormality stabilizes, resolves, or until a decision is made that it is not likely to resolve. If AEs of abnormal clinical laboratory test results do not return to Baseline within 30 days after the last dose given, their etiology should be identified and Ultragenyx should be notified. All unscheduled tests must be reported to Ultragenyx immediately.

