If a subject discontinues from the study prematurely, every reasonable effort should be made to perform the EoT Visit procedures within four weeks of discontinuation. If the subjects will be continuing KRN23 treatment under commercial use or another mechanism, all EoT assessments should be performed before beginning that treatment. For subjects not immediately continuing KRN23 treatment under commercial use or another mechanism, a Safety Follow-up TC will occur 4 weeks (+ 5 days) after the EoT visit to collect information on whether KRN23 treatment has been started through another mechanism and, if not, any ongoing or new AEs, SAEs, or concomitant medications. If the subject is not continuing KRN23 therapy under commercial use or another mechanism at that time, then site personnel will initiate a subsequent Safety Follow-up TC 8 weeks (+ 5 days) after the ET Visit to collect information on whether KRN23 treatment has been started through another mechanism and, if not, any ongoing or new AEs, SAEs, or concomitant medications.

Subjects who withdraw or are removed from the study after receiving study drug may be replaced on a case-by-case basis, at the discretion of Ultragenyx.

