7.4.5 Selection of Doses in the Study

A multiple-dose, dose escalation Phase 1/2 study (KRN23-INT-001) was conducted in adult XLH subjects. KRN23 was well tolerated following SC administration of 4 intra-subject escalating doses (0.05 mg/kg → 0.1 mg/kg → 0.3 mg/kg → 0.6 mg/kg) administered once per 28 days. The proportion of KRN23-treated subjects with serum phosphorus levels in the target range (>2.5 to \leq 3.5 mg/dL) increased with KRN23 dose level but did not exceed the ULN (4.5 mg/dL) in any subject at any time point. A direct PK-PD relationship between serum KRN23 concentrations and serum phosphorus levels was noted in the study. In an associated extension study (KRN23-INT-002), doses up to 1.0 mg/kg KRN23 administered monthly were well tolerated by adult XLH subjects over a period of 48 weeks.

Previous studies with KRN23 in adult XLH patients did not show any “off target” effects; therefore, the safety profile is expected to be related solely to the PD effect (i.e., increased serum phosphorus). Since the defined serum phosphorus target range in this study is well below the ULN, the likelihood of a dose-related safety issue is low (the target fasting peak serum phosphorus range for this study is \geq 2.5 to \leq 3.5 mg/dL [0.81 to 1.13 mmol/L]). The efficacy data on phosphate control from these previous studies also suggest there is a plateau in effect with KRN23 administered at dose levels between 0.60 mg/kg and 1.0 mg/kg. Dose adjustments will be individually titrated based on PD effects on serum phosphorus, safety, and tolerability.

The planned duration of treatment in this study is until the end of September 2018, ranging from 156-184 weeks (+5 days) depending on subject entry date.

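### The mandatory-withdrawal rule for prohibited medications (Protocol 7.5.3.3.1) still names a 144-week treatment period, but treatment now lasts 156 to 184 weeks

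*Protocol*

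**What the plan says.** The withdrawal rule is in Protocol section 7.5.3.3.1: "Any subject who resumes or requires the use of any of these medications during the 144-week treatment period will be discontinued from the study". The medications concerned are PTH suppressors, active vitamin D metabolites or analogs, phosphate, aluminum hydroxide antacids and any other monoclonal antibody.

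Elsewhere the current protocol gives a longer treatment period. Section 7.4.5 describes it as "ranging from 156-184 weeks (+5 days) depending on subject entry date". The synopsis states: "The treatment duration will be a maximum of 184 weeks (+ 5 days) with a maximum total of 46 doses administered". Section 7.1 puts the whole study at 164 to 192 weeks. In Table 2.2, Week 144 is an ordinary 24-weekly clinic visit, and the EoT Visit is the subject's last visit by 30 September 2018.

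The ban carries no week limit. The sentence just before the rule reads: "These medications will remain prohibited throughout the conduct of the study". Section 7.1 adds that subjects "may not resume any of those medications for the duration of the study".

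Section 7.3.3 is the general provision on removal. Its list opens with "Subjects may be removed from the study for the following reasons" and includes "Protocol deviation or noncompliance". The same section lets the investigator withdraw a subject at any time at his or her discretion.

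**The concern.** A ban and the consequence of breaking it are separate provisions. Here the ban runs for the whole study, while the fixed consequence is tied to a period that ends before any subject's planned treatment does. On the literal text, a subject who restarts phosphate at Week 140 must be withdrawn. One who restarts at Week 150 has broken the protocol, but the protocol does not say that withdrawal must follow. With up to 5 sites, two investigators could treat the same restart differently and each cite the protocol. What is at stake is consistent handling of a protocol violation late in treatment.

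**Working it through.** No power or sample-size formula applies. The check is whether the protocol's durations agree with each other, and by how much the rule falls short of them.

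**Reproducing the current duration**
- Maximum, from doses: 46 doses (synopsis) × 4 weeks = 184 weeks.
- Maximum, from study length: 192 weeks (7.1) − 8 weeks to the last follow-up call = 184 weeks.
- Minimum, from study length: 164 weeks (7.1) − 8 weeks = 156 weeks.

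All three match section 7.4.5. The figure of 144 weeks matches neither end of the range.

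**Time not covered on the literal reading**
- Shortest course: 156 − 144 = 12 weeks; 12/156 = 7.7%.
- Longest course: 184 − 144 = 40 weeks; 40/184 = 21.7%.

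**Doses given after Week 144.** Section 7.1 has doses every 4 weeks from Week 0 to the visit before EoT.
- EoT at Week 156: doses at Weeks 0 to 152, so 152/4 + 1 = 39. Those after Week 144 are at Weeks 148 and 152: 2 of 39 (5.1%).
- EoT at Week 184: doses at Weeks 0 to 180, so 180/4 + 1 = 46, which agrees with the synopsis. Those after Week 144 are at Weeks 148 to 180: 9 of 46 (19.6%).

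These counts leave out the dose at Week 144 itself. Including it gives 3 and 10.

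**Likely origin.** The summary of changes for Amendment 1 placed EoT at Week 144 and a follow-up call at Week 152. Amendment 2 then extended treatment. That history is not itself an inconsistency, but it explains the number. Section 8.5.4 still places the follow-up telephone call at Week 152, which looks like a leftover of the same kind.

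**The case against.** The strongest reply is that the rule refers to *the* treatment period and merely gets its length wrong; it does not say that it stops at Week 144. The preceding sentence keeps the medications prohibited throughout, exclusion criterion 7 covers use during the study, and nothing suggests an intention to relax the rule for the extension. This stands as the likely intent. But it works only by disregarding the number, and a withdrawal rule should not depend on that.

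A reader might infer that these medications become permitted after Week 144. The documents do not support this: sections 7.1, 7.5.3.3 and 7.5.3.3.1 all keep the ban.

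A reader might also infer an unmonitored safety gap, since serum phosphorus is scheduled only every 24 weeks at that stage. That interval has applied since Week 72 (7.5.1.1) and does not come from this wording. Several protections have no Week 144 limit:
- Table 2.2 marks concomitant medications at every visit type, including the 4-weekly home or telephone visits. Footnote 19 requires a call every 28 days (+5 days) for subjects dosing at home unsupervised.
- Doses may be reduced whenever phosphorus exceeds 4.5 mg/dL (7.4.6).
- A confirmed level of 6.5 mg/dL or more triggers review as a dose-limiting toxicity (7.5.3.13).
- New or worsening mineralization judged clinically meaningful and drug-related leads to discontinuation (7.3.3.1). Renal ultrasound and ECHO continue every 24 weeks.

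Sections 5.2.3 and 5.3 discuss excess phosphorus in nonclinical work and supplementation therapy separately. Neither reports on KRN23 given together with supplementation.

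**Conclusion.** The text is wrong as written, and the point is minor. An operative withdrawal rule carries a superseded duration. On a literal reading, mandatory withdrawal lapses for the last 12 of 156 to 40 of 184 weeks (2 of 39 to 9 of 46 doses), leaving only discretionary removal under section 7.3.3. On the reading that was probably intended there is no gap, only a wrong number.

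A reader might infer that the pharmacodynamic results are compromised. They are not, to any material degree. Section 7.6.4 says the study is not powered for any endpoint, and the SAP's primary statistical comparison (8.8.1) is Baseline against Week 72, well before the affected period. For a withdrawn subject, "every reasonable effort should be made to perform the EoT Visit procedures within four weeks of discontinuation", so a phosphorus value is expected either way. Keeping the subject adds at most one scheduled value: Week 168 plus EoT is 2, against 1 at EoT after withdrawal. Even that arises only if EoT falls at Weeks 172 to 184 and the restart comes before the Week 168 check.

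These counts assume that EoT falls on the 4-week grid, that doses are given as scheduled and that the EoT sample is obtained. The documents do not say how many of the 20 or so subjects might restart a prohibited drug, so no overall effect can be estimated.

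**What to change.** In section 7.5.3.3.1, replace the phrase that limits the rule to a 144-week period with: *at any time from Baseline through the EoT Visit*. This covers the whole treatment period, whatever the subject's entry date, and contains no figure that a later extension could make stale. Section 7.5.3.3 already ends the live-vaccine restriction at the EoT Visit in the same way.

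The cost is one phrase in the next amendment or in a clarification letter to sites. No visit, sample, procedure or analysis changes.

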7.5.3.3.2 Permitted Medications

Other than the medications specifically prohibited in this protocol, subjects may receive concomitant medications as required.

7.5.3.3.3 Constraints during the Course of the Study

Subjects are not permitted to change current diet or activity/exercise regimen from 1 week before dosing to the EoT evaluation. Alcohol intake will be permitted (up to 3 drinks per day) during the study duration.

7.5.3.4 Vital Signs

Vital signs (VS) will include seated systolic blood pressure (SBP) and diastolic blood pressure (DBP) measured in millimeters of mercury (mmHg), heart rate in beats per minute, respiration rate in breaths per minute, and temperature in degrees Celsius (°C). Vital sign measurements will be performed pre-dose at Week 0 and at the time points indicated in [Table 2.1](#) and [Table 2.2](#) before any additional assessments are completed. At each site visit, weight (in kilograms) will be obtained using a scale. Weight measurements will be used to calculate the appropriate KRN23 volume to be administered on a mg/kg basis.

All BP measurements will be made on the subject's non-dominant arm supported at heart level. If possible, vital signs should be taken by the same staff member, at the same time of day and by the same instrument at each visit.

7.5.3.5 Physical Examination

Physical examinations are to be performed by a qualified, licensed medical professional (i.e., MD, physician's assistant, or nurse practitioner), as designated by the investigator. Complete physical examinations will be performed pre-dose at Week 0 and at the time points indicated in [Table 2.1](#) and [Table 2.2](#). Physical examinations will include assessments of general appearance; head, eyes, ears, nose, and throat; and the cardiovascular, dermatologic, lymphatic, respiratory, gastrointestinal, genitourinary, musculoskeletal, and neurologic systems.

The genitourinary exam scope should be non-invasive and as per age-appropriate standard of care, at the investigator's discretion based on clinical judgement and/or safety need. If the PI determines there is no clinical indication for a genitourinary exam, it is not necessary to perform.

7.5.3.6 Clinical Laboratory Tests

Fasting for a minimum of 8 hours (overnight) is required prior to each blood draw; the duration of fasting will be recorded on the eCRF. Blood and urine samples will be collected at Screening, pre-dose at Baseline, and at regular intervals throughout the study, as indicated in [Table 2.1](#) and [Table 2.2](#). The local lab at the investigational sites will be used to assess safety parameters required for study eligibility (except FGF23). For the laboratory assessments collected at Screening, any results that fall outside the laboratory normal range will be considered abnormal and will be recorded in the medical history. The investigator will indicate whether laboratory test results are CS or NCS.

A comprehensive serum metabolic panel (Chem-20), complete blood count, and urinalysis will be used as routine screens to assess KRN23 safety. Certain analytes (i.e., ALP and serum phosphorus) in the routine Chem-20 panel are also designated as PD/efficacy parameters in this study (Section [7.5.1](#)). KRN23/XLH biochemical parameters of interest include serum amylase, lipase, total calcium, creatinine, FGF23, and iPTH; and urinary calcium and creatinine. Reflexive testing for amylase isoenzymes will be performed if serum amylase levels are elevated by ≥ 1.5 the upper limit of the reference range. FGF23 concentrations will be measured using validated assays.

Twenty-four hour urine collection is required to assess urinary phosphorus:creatinine and calcium:creatinine ratios; urinary phosphorus (a PD parameter, Section [7.5.1.1](#)) will also be obtained from 24-hour urine samples. The fasting 2-hour urine collection (collected in conjunction with the 24-hour urine collection) is also required, to determine TmP/GFR levels. The 2-hour and 24-hour urine collection will be performed at Screening for TmP/GFR eligibility and at Weeks 12, 24, 36, 48, 72, 96, 120, 144, and every 24 weeks as applicable.

through the EoT Visit as indicated in [Table 2.1](#) and [Table 2.2](#). Results obtained at Screening will serve as Baseline data.

Clinical laboratory parameters to be assessed for safety are provided in [Table 7.5.3.6.1](#). See the Study Reference Manual for details on sample collection and processing.

Table 7.5.3.6.1: Clinical Laboratory Assessments

Chemistry	Hematology	Urinalysis
1,25(OH) ₂ D	Hematocrit	Appearance
Alanine aminotransferase (ALT)	Hemoglobin	Color
Alkaline phosphatase (ALP)*	Platelet count	pH
Amylase	Red blood cell (RBC) count	Specific gravity
Amylase isoenzymes [†]	White blood cell (WBC) count	Ketones
Aspartate aminotransferase (AST)	Mean corpuscular volume (MCV)	Protein
Bone-specific ALP (BALP)*	Mean corpuscular hemoglobin (MCH)	Glucose
Bilirubin (direct and total)	MCH concentration	
Blood urea nitrogen (BUN)		24-hour Urine
Calcium (total)		Calcium
Chloride		Calcium/creatinine ratio
Carbon dioxide (CO ₂)		Creatinine
Cholesterol (total) and triglycerides		Phosphorus
Creatinine		Phosphorus/creatinine ratio
Carboxy terminal cross-linked telopeptide of type I collagen (CTX)		
Gamma-glutamyl transpeptidase (GGT)		2-hour Urine
Glucose		Calcium
FGF23		Creatinine
Intact parathyroid hormone (iPTH)*		Calcium/creatinine ratio
Lactate dehydrogenase (LDH)		Phosphorus
Lipase		TmP/GFR
Phosphorus*		Pregnancy Test (if applicable)
Potassium		
Procollagen type 1 N-terminal propeptide (P1NP)*		
Protein (albumin and total)		
Sodium		
Uric acid		

*Also designated as PD/efficacy parameter

† Will be assessed reflexively if amylase levels are ≥ 1.5 times the upper limit of the reference range

The following laboratory abnormalities should be captured on the SAE form and/or eCRF, as appropriate:

- Any laboratory test result that meets the criteria for an SAE
- Any laboratory abnormality that requires the subject to have study medication discontinued or interrupted
- Any laboratory abnormality that requires the subject to receive specific corrective therapy

Any clinically significant abnormal laboratory tests occurring during the study will be repeated at appropriate intervals until 1 or more of the following occur:

- The value returns to Baseline
- The value is judged to be clinically acceptable by the investigator and the sponsor
- A diagnosis is reached that explains the abnormal laboratory value

Whenever possible, the investigator should report the clinical rather than the laboratory term (e.g., anemia, vs. low hemoglobin [Hb]).

Subjects who experience an SAE possibly or probably related to study drug or other AE of concern may, at the discretion of the investigator (and/or medical monitor), have additional blood samples taken for safety laboratory tests.

